9.4.1.2 Primary Analysis

The primary analysis for the dose exploration phase will occur when target enrollment is complete and each subject either completes 6 months on the study or withdraws from the study.

The primary analysis for the study will occur when target enrollment is complete for the dose expansion phase and each subject either completes 1 year on study or withdraws from the study.

9.4.1.3 Final Analysis

The final analysis will occur when target enrollment is complete for both phases and all subjects have ended the study.

9.4.2 Methods of Analyses

9.4.2.1 General Considerations

Descriptive statistics will be provided for selected demographics, safety, PK, efficacy, [REDACTED] by dose, dose schedule, and time as appropriate. Descriptive statistics on continuous data will include means, medians, standard deviations and ranges, while categorical data will be summarized using frequency counts and percentages. Graphical summaries of the data may also be presented.

Confidence intervals (CI) for proportions will be estimated using an exact method proposed by Clopper-Pearson (Clopper and Pearson, 1934). Kaplan-Meier methods will be used to estimate the median and percentiles for time to event endpoints with CI calculated using the Brookmeyer and Crowley (Brookmeyer and Crowley, 1982) method. Kaplan-Meier methods will be used to estimate landmarks for time to event endpoints (eg, 1-year overall survival [OS]) with the Greenwood formula (Kalbfleisch and Prentice, 1980) used to estimate the standard error used in CI calculation.

9.4.2.2 Efficacy Analyses

Endpoint	Statistical Analysis Methods
Primary	Not applicable.
Secondary	Listings of secondary efficacy endpoints will be produced for all subjects. The proportion of subjects with an OR (per modified RECIST 1.1) and 95% CI will be tabulated by planned dose level. For all subjects treated at the MTD and/or RP2D, Kaplan-Meier methods will be used to estimate the time to event curve, median time to event and percentiles with 95% CI for 1) duration of response; 2) time to progression; 3) progression-free survival; 4) time to subsequent therapy; 5) overall survival; 6) time to response. For all subjects treated at the MTD and/or RP2D, Kaplan-Meier methods will be used to estimate landmarks for time to event endpoints (eg, 1-year PFS) with 95% CI).

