6.1 Safety Analysis Set

The analysis of all endpoints, unless noted otherwise, will be conducted on the Safety Analysis Set defined as all subjects that are enrolled and receive at least 1 dose of AMG 160.

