6.2 RECIST 1.1 Evaluable Analysis Set

RECIST 1.1 Evaluable Analysis Set is defined as all subjects that are enrolled, receive at least 1 dose of investigational product (AMG 160) and have measurable baseline disease per RECIST 1.1 per protocol and have the opportunity to be followed for at least 9 weeks starting from Study Day 1. Subjects who stopped disease assessment prior to 9 weeks will be included in this analysis set if the data cutoff is at least 9 weeks after their Study Day 1.

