9.1 General Considerations

Descriptive statistics will be provided for selected demographics, safety, PK, efficacy, [REDACTED] by dose, dose schedule, and time as appropriate. Descriptive

statistics on continuous data will include means, medians, standard deviations and ranges, while categorical data will be summarized using frequency counts and percentages. Graphical summaries of the data may also be presented.

Confidence intervals (CI) for proportions will be estimated using an exact method proposed by Clopper-Pearson ([Clopper and Pearson, 1934](#)). Kaplan-Meier methods will be used to estimate the median and percentiles for time to event endpoints with CI calculated using the Brookmeyer and Crowley ([Brookmeyer and Crowley, 1982](#)) method. Kaplan-Meier methods will be used to estimate landmarks for time to event endpoints (eg, 1-year overall survival [OS]) with the Greenwood formula ([Kalbfleisch and Prentice, 1980](#)) used to estimate the standard error used in CI calculation.

Greenwood formula will be used for landmark analysis, and for other time-to event analysis the Brookmeyer and Crowley formula will be used. We will be only doing the landmark analysis for OS.

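### SAP Table 9-1 drops the protocol's MTD/RP2D restriction, by-dose ORR table and PFS landmarks, and Section 10 does not declare it

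*Protocol*

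**What the plan says.** Protocol 9.4.2.2 makes three commitments on the secondary efficacy endpoints, none of them qualified:

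- **ORR:** "The proportion of subjects with an OR (per modified RECIST 1.1) and 95% CI will be tabulated by planned dose level".
- **Time-to-event endpoints** (duration of response, time to progression, PFS, time to subsequent therapy, OS, time to response): "For all subjects treated at the MTD and/or RP2D, Kaplan-Meier methods will be used to estimate the time to event curve".
- **Landmarks**, for that same population: "Kaplan-Meier methods will be used to estimate landmarks for time to event endpoints (eg, 1-year PFS) with 95% CI".

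SAP 9.5.2, Table 9-1, gives each endpoint an analysis set. OS, radiographic and clinical PFS, radiographic and clinical time to progression, and time to subsequent therapy go to the "Safety Analysis Set defined as all subjects that are enrolled and receive at least 1 dose of AMG 160" (SAP 6.1). ORR, time to response and duration of response go to the RECIST 1.1 Evaluable Analysis Set. SAP 6.2 builds that set from all enrolled subjects with at least one dose, and adds measurable baseline disease and the opportunity for 9 weeks of follow-up. Neither set is limited by dose, and Table 9-1 contains no dose restriction and no dose-level tabulation.

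SAP Appendix C defines ORR as responders divided by everyone in the analysis set. SAP 9.1 provides for efficacy descriptive statistics by dose where appropriate. It repeats the protocol's general landmark sentence, then adds: "We will be only doing the landmark analysis for OS".

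SAP Section 10 lists two changes from the protocol: the added RECIST 1.1 Evaluable Analysis Set, and the removal of the rPFS name.

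**The concern.** The two documents give different populations for the same endpoints, and the section meant to record departures is silent on it. A programmer working from Table 9-1 would produce one all-dose ORR and all-dose Kaplan-Meier curves. A reader of the protocol would expect results at the selected dose.

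This matters because the design mixes doses. Dosing starts one level below the RP2D of Study 20180101 and may go up or down (Protocol 6.2.1.1, 9.2). Up to 20 backfill subjects may enter at one or more levels (9.2). The squamous expansion cohort may be treated at a lowered dose (4.1). Part 2 is run at the MTD/RP2D identified in Part 1, so that dose is the one whose activity the expansion is meant to describe. An all-dose ORR or median PFS may describe no single dose. If by-dose display is decided only as appropriate, the choice can also be made after the data are seen.

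**Working it through.** **1. The plan's own figure.** Protocol 9.2 and SAP 3.2 give an expected exact 95% CI of 9% to 36% for 40 subjects with a 20% response rate. Clopper-Pearson for 8/40 gives 9.05% to 35.65%, so the figure is reproduced. It describes the 40 expansion subjects, not an all-dose set.

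**2. The texts side by side.**

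| Item | Protocol 9.4.2.2 | SAP | Declared in SAP Section 10? |
|---|---|---|---|
| OS, PFS, time to progression, time to subsequent therapy | Subjects treated at MTD and/or RP2D | Safety Analysis Set, all doses | No |
| Time to response, duration of response | Subjects treated at MTD and/or RP2D | RECIST 1.1 Evaluable set, all doses | Set: yes. Loss of dose restriction: no |
| ORR | By planned dose level | One proportion over the whole RECIST set | Set: yes. Loss of by-dose table: no |
| Landmarks | Time-to-event endpoints, 1-year PFS as example | OS only | No |

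The SAP does name dose level elsewhere: DLT incidence is by planned dose level (Table 9-3) and PK parameters are by dose level (9.7.1). The efficacy table has no such wording.

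**3. How far an all-dose ORR could differ (illustration only).** The documents give no response rates by dose. Assume 40 subjects at the RP2D with ORR 20% (8 responders), plus *m* subjects at other doses with ORR *q*:

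all-dose ORR = (8 + *m* × *q*) / (40 + *m*)

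| *m* at other doses | *q* = 0% | *q* = 10% | *q* = 20% |
|---|---|---|---|
| 10 | 8/50 = 16.0% | 9/50 = 18.0% | 10/50 = 20.0% |
| 20 | 8/60 = 13.3% | 10/60 = 16.7% | 12/60 = 20.0% |
| 30 | 8/70 = 11.4% | 11/70 = 15.7% | 14/70 = 20.0% |

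The case *m* = 30 is an extreme: all 10 exploration and all 20 backfill subjects at doses other than the RP2D. The range is 11.4% to 20%.

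**4. Effect on the interval.** With *q* = 0 the exact 95% CI is 7.2% to 29.1% for 8/50 and 5.1% to 21.3% for 8/70, against 9.1% to 35.6% for 8/40. Adding other doses can move the interval and also make it look more precise about the RP2D than it is.

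No corresponding figure can be given for the Kaplan-Meier endpoints, because the documents state no event-time assumptions by dose.

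**The case against.** A reader might infer that the SAP orders all doses to be pooled and rules out results by dose. The text does not go that far. The SAP never says so; Table 9-1 assigns analysis sets and does not say how results are grouped. SAP 9.1 allows by-dose efficacy statistics, and Protocol 9.4.2.1 carries the same sentence. The SAP's general rule, "The analysis of all endpoints, unless noted otherwise, will be conducted on the Safety Analysis Set", also stands in Protocol 9.3.1, so using that set does not by itself show a departure. SAP Section 1 says the plan details analyses outlined in protocol amendment 4, which could be read as leaving 9.4.2.2 in force.

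These points limit the wording but do not remove the conflict. The protocol carried the same two general sentences and still added the specific commitments in 9.4.2.2. The SAP keeps the general sentences and omits the specific ones.

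A reader might also infer that Section 10 discloses nothing relevant. It does declare the RECIST set, so the change of set for ORR, time to response and duration of response is disclosed. The loss of the dose restriction is not.

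A third tempting step is to state a definite dilution. That would need response rates and dose splits that the documents do not give. Only the first 2 to 4 subjects are planned for Dose Level 1, and backfill may be at the RP2D itself.

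Further points that stand: the stated objective is preliminary activity of AMG 160, not activity at one dose; the futility rule counts responders without a dose restriction, so a cross-dose ORR is not foreign to the design; and 1-year PFS is only an example in the protocol, with PFS still receiving a Kaplan-Meier curve, median and percentiles in the SAP. The landmark item is therefore minor.

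**Conclusion.** The point holds as an undeclared mismatch between protocol and SAP. The protocol commits to MTD/RP2D populations for Kaplan-Meier estimates and landmarks, and to ORR by planned dose level. The SAP makes all-dose estimates the default, leaves by-dose display to discretion, keeps landmarks for OS only, and records none of these three changes.

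The numerical consequence is unknown. Under the assumptions in the working, the all-dose ORR would lie between 11.4% and 20% when the RP2D rate is 20%. The difference is nil if activity is equal across doses or if no subjects were treated at other doses. The mismatch exists either way.

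These are secondary, descriptive endpoints and no hypothesis is tested. The matter should be corrected, but it does not undermine the trial's primary safety objective.

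**What to change.** In SAP 9.5.2 and Table 9-1:

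- present the time-to-event endpoints for subjects treated at the MTD and/or RP2D;
- tabulate ORR with its exact 95% CI by planned dose level;
- keep the all-dose results on the present analysis sets as supportive.

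In SAP 9.1, either restore landmark PFS with its CI, or list its removal with a reason in Section 10. If the sponsor prefers all-dose estimates as the main results, Section 10 should say so for each endpoint and give the reason.

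This needs only SAP wording and some added table shells, with no new data. The price is a smaller n and wider intervals for the headline estimates. In the illustration, that means 9.1% to 35.6% on 40 subjects instead of 5.1% to 21.3% on 70. The wider interval reflects the information available at that dose.

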9.4.2.3 Safety Analyses

9.4.2.3.1 Analyses of Primary Safety Endpoint(s)

Endpoint	Statistical Analysis Methods
Primary	Unless otherwise specified, statistical analyses on safety endpoints will be done using subjects from the safety analysis set, which includes subjects that are enrolled and received AMG 160. The analysis of DLTs will be conducted on the DLT Analysis Set. Subject incidence of DLT will be tabulated by planned dose level. The statistical analysis methods for other safety endpoints are in Section 9.4.2.3 below.

9.4.2.3.2 Adverse Events

Subject incidence of all treatment-emergent adverse events will be tabulated by system organ class and preferred term and grade. Tables of fatal adverse events, serious adverse events, adverse events leading to withdrawal from investigational product or other protocol-required therapies, and significant treatment emergent adverse events will also be provided. A subgroup analysis of safety with CRS outcome and PK will be performed for subjects who were administered siltuximab.

9.4.2.3.3 Laboratory Test Results

Clinical chemistry, hematology, and urinalysis data will be reviewed for each subject. Depending on the size and scope of changes in laboratory data the analyses of safety laboratory endpoints will include summary statistics over time and/or changes from baseline over time may be provided. Shifts in grades of safety laboratory values from baseline for selected laboratory values may also be provided

9.4.2.3.4 Vital Signs

Vital signs data will be reviewed for each subject. The analyses of vital signs will include summary statistics over time and/or changes from baseline over time may be provided.

9.4.2.3.5 Physical Measurements

Physical measurements will be reviewed for each subject.

9.4.2.3.6 Electrocardiogram

Summaries over time and/or changes from baseline over time will be provided for all ECG parameters. Subjects' maximum change from baseline in QTcF will be categorized and the number and percentage of subjects in each cohort will be summarized.

Subjects' maximum post baseline values will also be categorized and the number and percentage of subjects in each cohort will be summarized. All on-study ECG data will be listed and select parameters of interest plotted.

9.4.2.3.8 Exposure to Investigational Product

Details of AMG 160 administration will be listed for every subject.

9.4.2.3.9 Exposure to Non-investigational Product

Subject-level data may be provided instead of the summary if the subject incidence is low or single dose is given. The number of days on non-investigational product, the daily dose, and the proportion of subjects receiving each dose level will be summarized using descriptive statistics.

Compliance with non-investigational product will be summarized for each subject using descriptive statistics.

9.4.2.3.10 Exposure to Other Protocol-required Therapy

Descriptive statistics of total dose (mg/kg), total dose (mg), average daily dose, cumulative dose and number of cycles will be produced to describe the exposure to AMG 160 by planned dose level.

9.4.2.3.11 Exposure to Concomitant Medication

Number and proportion of subjects receiving therapies of interest will be summarized by preferred term or category for each treatment group as coded by the World Health Organization Drug dictionary.

9.4.2.4 Other Analyses

Pharmacokinetic parameters will be determined from the time concentration profile using standard non-compartmental approaches and considering the profile over the complete sampling interval. [REDACTED]

[REDACTED]

[REDACTED]

[REDACTED].

10. References

American Cancer Society. Cancer Facts & Figures. Atlanta, Ga: American Cancer Society; 2020.

AMG 160 Investigator's Brochure. Thousand Oaks, CA. Amgen Inc.

Arbour KC and Riely GJ. Systemic Therapy for Locally Advanced and Metastatic Non-Small Cell Lung Cancer: A Review. *JAMA*. 2019;322:764-774.

BLINCYTO® (blinatumomab) United States Prescribing Information. Thousand Oaks, CA. Amgen, Inc., 2018.

Bristol-Myers Squibb Company. Opdivo (nivolumab): Highlights of Prescribing Information. 2018.

Dirks NL and Meibohm B. Population Pharmacokinetics of Therapeutic Monoclonal Antibodies. *Clin Pharmacokinet*. 2010;49:633-659.

11.1 Appendix 1. List of Abbreviations and Definitions of Terms

Abbreviation or Term	Definition/Explanation
ADR	adverse drug reaction
ALK	anaplastic lymphoma kinase
ALL	acute lymphoblastic leukemia
ALP	alkaline phosphatase
ALT	alanine aminotransferase
aPTT	activated partial thromboplastin time
AST	aspartate aminotransferase
AUC	area under the concentration-time curve
BiTE	bispecific T-cell engager
C _{max}	maximum serum concentration
C _{min}	minimum serum concentration
CAR-T	chimeric antigen receptor T cells
CD	cluster of differentiation
CFR	U.S. Code of Federal Regulations
CI	confidence intervals
COVID-19	coronavirus disease 2019
CNS	central nervous system
CR	complete response
CRF	case report form
CRS	cytokine release syndrome
CT	computed tomography
CTCAE	Common Terminology Criteria for Adverse Events
CTC0	circulating tumor cell zero
DILI	drug-induced liver injury
DLRM	dose level review meeting
DLRT	dose level review team
DLT	dose-limiting toxicities
ECG	electrocardiogram
ECHO	echocardiogram
ECOG	Eastern Cooperative Oncology Group
eCRF	electronic case report form
EDC	electronic data capture
EEG	electroencephalogram

Abbreviation or Term	Definition/Explanation
EGFR	epidermal growth factor receptor
EMA	European Medicines Agency
Electronic Source Data (eSource)	source data captured initially into a permanent electronic record used for the reconstruction and evaluation of a trial.
End of Follow-up	defined as when the last subject completes the last protocol-specified assessment in the study
EOI	end of infusion
End of Study for Individual Subject	defined as the last day that protocol-specified procedures are conducted for an individual subject
End of Study (primary completion)	defined as the date when the last subject is assessed or receives an intervention for the final collection of data for the primary endpoint(s), for the purposes of conducting the primary analysis, whether the study concluded as planned in the protocol or was terminated early
End of Study (end of trial)	defined as the date when the last subject across all sites is assessed or receives an intervention for evaluation in the study (ie, last subject last visit), following any additional parts in the study (eg, long-term follow-up), as applicable
End of Treatment	defined as the last assessment for the protocol-specified treatment phase of the study for an individual subject
FDA	Food and Drug Administration
FFPE	formalin-fixed paraffin-embedded
FIH	first in human
FSH	follicle stimulating hormone
⁶⁸ Ga	⁶⁸ Gallium
G-CSF	granulocyte colony stimulating factor
GCP	Good Clinical Practice
GI	gastrointestinal
GSO	Global Safety Officer
HIV	human immunodeficiency virus
HLE	half-life extended
HNSTD	highest nonseverely toxic dose
HRT	hormone replacement therapy
ICANS	immune-effector cell associated neurologic syndrome
ICE	immune effector cell associated encephalopathy
ICF	informed consent form
ICH	International Council for Harmonisation
ICP	intracranial pressure
IEC	Independent Ethics Committee

Abbreviation or Term	Definition/Explanation
Ig	immunoglobulin
IL-6	interleukin-6
INR	international normalized ratio
IPIM	Investigational Product Instruction Manual
IRB	Institutional Review Board
IRT	interactive response technology that is linked to a central computer in real time as an interface to collect and process information
IUD	intrauterine device
IV	intravenous
mCRPC	metastatic castration-resistant prostate cancer
MRI	magnetic resonance imaging
MTD	maximum tolerated dose
mTPI	modified toxicity probability interval
MUGA scan	multigated acquisition scan
NA	not available
NCT	National Clinical Trials
ND	not done
NTRK	neurotrophic tropomyosin-related kinase
NSCLC	non-small cell lung cancer
OR	objective response(s)
ORR	objective response rate
OS	overall survival
PCWG3	Prostate Cancer Working Group 3
PD	disease progression
PD1	programmed cell death protein 1
PDL1	programmed death-ligand 1
PET	positron emission tomography
PFS	progression-free survival
PK	pharmacokinetic(s)
PO	orally
PR	partial response
PS	performance status
PSA	prostate specific antigen

Abbreviation or Term	Definition/Explanation
PSMA	prostate-specific membrane antigen
rPFS	progression-free survival (radiographic)
RECIST	Response Evaluation Criteria in Solid Tumors
RR	relapsed/refractory
RP2D	recommended phase 2 dose
RT-PCR	reverse transcriptase-polymerase chain reaction
SAg	surface antigen
SAP	statistical analysis plan
SARS-CoV-2	severe acute respiratory syndrome coronavirus 2
scFc	single chain fragment crystallizable
SC	subcutaneous
SD	stable disease
SLD	sum of the longest diameters
Source Data	information from an original record or certified copy of the original record containing patient information for use in clinical research. The information may include, but is not limited to, clinical findings, observations, or other activities in a clinical trial necessary for the reconstruction and evaluation of the trial. Source data are contained in source documents (original records or certified copies). (ICH Guideline [E6]). Examples of source data include Subject identification, Randomization identification, and Stratification Value.
Study Day 1	defined as the first day that protocol-specified investigational product(s)/protocol-required therapies is/are administered to the subject
$t_{1/2}$	half-life
TBL	total bilirubin
TLS	tumor lysis syndrome
TPI	toxicity probability intervals
TPS	tumor proportion score
TNF	anti-tumor necrosis factor
UE	unable to evaluate
ULN	upper limit of normal

11.2 Appendix 2. Clinical Laboratory Tests

The tests will be performed by the local laboratory or by the central laboratory (Table 11-1). Additional analyte test results may be reported by the local or central laboratory, in accordance with standard laboratory procedures (eg, components of a hematology panel).

Protocol-specific requirements for inclusion or exclusion of subjects are detailed in Sections 5.1 to 5.2 of the protocol.

Additional tests may be performed at any time during the study as determined necessary by the investigator or required by local regulations.

Table 11-1. Laboratory Analyte Listing

LOCAL LABORATORY				
Chemistry		Urinalysis	Hematology	Coagulation
sodium	creatinine	specific gravity	RBC	aPTT
potassium	uric acid	pH	hemoglobin	PT/INR
chloride	total bilirubin	blood	hematocrit	fibrinogen
bicarbonate	direct bilirubin	protein	reticulocytes	D-dimer
total protein	AST (SGOT)	glucose	platelets	
albumin	ALT (SGPT)	bilirubin	WBC differential:	
calcium	ALP	WBC	• neutrophils	
adjusted calcium	LDH	RBC	• bands/stabs (if available)	
magnesium	CRP	epithelial cells	• segmented neutrophils (if available)	
phosphorus	ferritin	bacteria	• eosinophils	Other Labs
glucose	eGFR ^a	casts	• basophils	Pregnancy test
BUN or urea		crystals	• lymphocytes	
			• monocytes	
			ANC	
CENTRAL LABORATORY				
PK collection				

ALT=alanine aminotransferase; ALP = alkaline phosphatase; ANC = absolute neutrophil count; aPTT = activated partial thromboplastin time; AST = aspartate aminotransferase; BUN = blood urea nitrogen; Cr = creatinine; CRP = C-reactive protein; [REDACTED]; eGFR = estimated glomerular filtration rate; HRR = homologous recombination repair; INR = international normalized ratio; LDH = lactate dehydrogenase; MDRD = Modification of Diet in Renal Disease; [REDACTED] PK = pharmacokinetics; PSMA = prostate-specific membrane antigen; PT = prothrombin time; RBC = red blood cell count; SGOT = serum glutamic-oxaloacetic transaminase; SGPT = serum glutamic-pyruvic transaminase; WBC = white blood cell

^a eGFR will be based on Modification of Diet in Renal Disease (MDRD) equation (Levey et al, 1999):

- $eGFR = 186 \times (\text{Serum Cr}^{-1.154}) \times (\text{age}^{-0.203}) \times 1.212$ (if subject is black) $\times 0.742$ (if subject is female)
- use serum creatinine (Cr) in mg/dL for this formula

